# **REVISION HISTORY**

Revision	Version Date	Summary of Changes
#		
1	November 22, 2022	A sixth visit for the Foster Care Advisory Board group has been added, and the compensation structure has been updated. Foster Care Advisory Board members will receive up to \$250 for attending all six meetings.
2	April 10, 2023	Adjusting age for eligibility criteria from 2-5 years to 2-8 years.  Adding more specific detail as to what caregiver-report measures will be completed during the CPP-FC pilot.
3	May 30, 2023	We are requesting a waiver for collecting participant Social Security Numbers and W9s. Over 30% of the potentially eligible participants we have recruited have declined participation due to not wanting to provide their Social Security Number or complete a W9 form. Because the compensation for this phase of the study is not more than \$100, we feel that a waiver is warranted.
4	July 21, 2023	Due to successful recruitment for our pilot phase, we are adding a third pilot cohort. We enrolled n = 5 participants into our first pilot cohort, and n = 11 into our second pilot cohort, of which n = 5-6 will instead participate in the third pilot cohort.
5	September 7, 2023	We are requesting to add \$5 compensation per session for participant attendance. We also added clarifying language for compensation and completion of homework, as well as including more than one caregiver in the same household in qualitative interviews.
6	October 4, 2023	In the event that an end-of-program qualitative interview runs beyond 60 minutes, and not all parties are able to continue the interview at that time, we will schedule a time with the participant to complete the remainder of the interview. We will reimburse participants an additional \$10 if the interview lasts longer than 60 minutes, whether it occurs in one

	or two sessions. We anticipate most interviews will not run longer than
	60 minutes.

# 1.0 Study Summary

Study Title	Adapting Chicago Parent Program for the Foster Care Setting
Study Design	This study involves administration of an evidence-based prevention
	program to prevent and reduce behavior problems in children (Chicago
	Parent Program; CPP). CPP content will be delivered to foster and kinship
	caregivers who are members of a Foster Caregiver Advisory Board. The
	Foster Caregiver Advisory Board will provide feedback and guide the
	development of CPP adapted for foster care (CPP-FC) in collaboration with
	the research team. Adapted content will be delivered to three cohorts of
	foster caregivers virtually in 11 synchronous weekly sessions and 1
	booster session with two trained facilitators. Facilitators use video
	vignettes, handouts, and role play during sessions to support content
	delivery and engage parents in material. We will adapt CPP by creating
	additional handouts, discussion questions, and topics that contextualize
	CPP material to foster care, to meet the needs and social norms of foster
	caregivers. Adaptations will not modify the core components of CPP
	known to impact caregiver and child outcomes. Data for this study will
	come from multiple sources, including caregiver participant report, and
	review of existing electronic databases at CCHMC.
Primary Objective	The primary aim of this study is to deliver and adapt Chicago Parent
	Program for the foster care setting and pilot adapted content in three
	cohorts of foster caregivers.
Secondary Objective(s)	The secondary objective of this study is to gather preliminary data for a
	later clinical trial of CPP that has been adapted for the foster care setting
	(CPP-FC).
Research	The Chicago Parent Program adapted for foster care (CPP-FC)
Intervention(s)/	
Investigational Agent(s)	
IND/IDE #	None
Study Population	Adults who are either licensed foster caregivers or kinship caregivers to
	children in foster care.
Sample Size	Foster Care Advisory Board, N = 6; CPP-FC Pilot, N = 12-16
Study Duration for	Approximately 32 weeks
individual participants	
Study Specific	Chicago Parent Program (CPP)
Abbreviations/	Parents on Point (PoP)
Definitions	

### 2.0 Objectives

#### 2.1 Purpose and objectives

The purpose of this study is to adapt the content of Chicago Parent Program (CPP) for the foster care setting (CPP-FC) in collaboration with a foster caregiver advisory board, and to pilot the adapted CPP-FC content with three cohorts of foster caregivers. Participants will be caregivers to a child in foster care between the ages of 2 and 8 years.

The Chicago Parent Program (CPP) is an evidence-based 12-session program designed for families raising young children in low-income settings. CPP was designed with an advisory council of African American and Latinx low-income parents and has since demonstrated significant and sustained improvements in consistent discipline, parenting self-efficacy, and child behavior problems 1 year following training in randomized studies with more than 500 minority parent-child dyads. CPP utilizes best practices for retention and engagement of hard-to-reach populations including employing trainers from a variety of backgrounds, featuring diverse individuals in video vignettes, using interactive training methods (role play, group discussion) and a focus on real world application (practice assignments). If available to foster caregivers, CPP could prevent or reduce behavior problems in foster youth, increase self-efficacy and consistent discipline with caregivers, and prevent unnecessary placement changes. Further, CPP can be delivered synchronously using virtual platforms, which addresses barriers faced by foster caregivers (i.e., competing activities, childcare and transportation challenges). However, tailoring of the existing program is necessary. Unlike custodial parents, relationships between foster caregivers and children must be established, and the foster care setting introduces additional challenges (e.g., maltreatment histories in children, lack of shared family routines). It is unknown whether those differences create barriers that foster and kinship families perceive as limitations to accessing and utilizing CPP.

# 2.2 Study aims

The primary aim of this study is to adapt CPP to meet the unique needs of children ages 2-8 years who are placed with foster and kinship caregivers, and pilot delivery coordinated with mandated healthcare visits. CPP will be adapted (e.g., additional content regarding trauma and child maltreatment, modified discussion of vignettes, additional role-play targeting specific foster care scenarios) while maintaining core elements integral to the program. The ensure validity, generalizability, and relevance a stakeholder adaptation team of 6 caregivers has been established to guide development of adapted content.

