culturally and contextually relevant and engaging for parents and caregivers from diverse backgrounds, particularly to the needs of African American and Latinx families. This is a noteworthy feature that is absent from other parenting support approaches. The primary goals of CPP are to improve parent-child relationships, increase consistency in parenting behavior, reduce use of harsh discipline, promote parent confidence and skills in managing behaviors, expand the social support network for parents through the group meetings, and prevent and reduce children's behavior problems as a result.  This is accomplished in 12 two-hour group sessions facilitated by two trained group leaders who use multiple parent education strategies. The egalitarian group structure and use of group facilitators from the same community as participants (as opposed to interventionists identified as "experts") provides a safe and supportive space in which to discuss challenging issues related to parenting. Leveraging theories regarding small groups and behavior change and robust evidence linking video vignettes to promote content acceptability, CPP is offered in a group format of 10-15 parents. 33-36 The group format encourages parents to connect with each other, and form relationships that may continue outside of the group. Content delivery methods include (1) brief video vignettes of parents and children engaged in real-life challenging situations at home and in public settings (e.g., grocery stores, laundromats, etc.); (2) discussion questions tied to the vignettes that are designed to highlight key principles and strategies relevant to the session topic; (3) role play and group activities designed to help parents try out new skills and receive feedback and support; (4) list making activities intended to help parents clarify their goals and values relevant to the session topic; (5) weekly handouts summarizing key messages from each session; and (6) weekly practice assignments designed to help parents apply the new skills with their children. After each session, parents receive a "practice assignment" designed to help parents practice the new skill with their child during the week. Practice assignments are reviewed at the beginning of each session and preparation for practice is discussed at the end of each session. Parents submit a practice checklist noting which and how much of the assignment they were able to complete.

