CPP-FC Pilot Procedures. Once CPP-FC is prepared, three cohorts of foster caregivers (6-8 families per cohort) will be recruited to complete CPP-FC in synchronous virtual sessions. Recruitment strategies will maximize inclusion of African American and Latinx families. Two facilitators trained in CPP and CPP-FC who are familiar with the child welfare system will deliver the 12 sessions. When possible, trained facilitators who have experience as caseworkers, kinship or licensed caregivers, or other child welfare experience will be used. The purpose of this pilot phase is to ensure that adapted materials are acceptable to foster families, that the order of materials being delivered is logical and sound, that caregiver engagement with materials is high, and that facilitators find it feasible to deliver. At baseline, after each session, and at the end of CPP-FC, participating caregivers will complete surveys assessing their satisfaction with the program, their stress and confidence in managing behavior problems, and the behaviors of children in their homes (see 4.3 Study measures).

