Caregiver-report measures administered at baseline and end of program include the Perceived Stress Scale, Child Adjustment and Parent Efficacy Scale (CAPES), Parenting Sense of Competence Scale, Eyberg Child Behavior Inventory, Strengths and Difficulties Questionnaire, and the Parental Stress Scale.

**CPP-FC end of session measures.** At the end of each CPP-FC session, caregiver participants will complete surveys on satisfaction with session material, as well as weekly homework assignments. Following sessions 4, 8, and 12, participants will also complete the Group Environment Scale.

**CPP-FC end of program measures.** At the end of the CPP-FC program, caregiver participants will complete surveys assessing program satisfaction, caregiver stress, caregiver confidence, child behavior, and receipt of child developmental, medical, and behavioral health services. In the event that the child has changed placements during the study, the caregiver will continue to participate and give feedback on program content but will not report on child behavior at this follow-up. Caregiver participants and any additional caregivers residing in the same home who attended one or more CPP-FC sessions

will also complete a semi-structured interview approximately 45 minutes in length, facilitated by the research team and report on strengths and difficulties of CPP-FC, impact of CPP-FC, and feedback on how to further adapt and improve CPP-FC content.

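### No listed pilot measure records what facilitators delivered, so retention of CPP's core components in delivery cannot be verified and facilitator feasibility has no data source

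*Combined protocol and SAP*

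**What the plan says.** Section 2.2 says that CPP will be adapted "while maintaining core elements integral to the program". Section 1.0 gives the same assurance: "Adaptations will not modify the core components of CPP". The adaptation both adds and modifies. Sections 1.0, 2.2 and 4.3 (Table 1) list new handouts, topics, discussion questions, role plays and trauma content, together with changed discussion of the existing vignettes.

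The number of sessions does not change. Section 2.1 describes CPP as "an evidence-based 12-session program designed for families". Section 1.0 has CPP-FC delivered to "foster caregivers virtually in 11 synchronous weekly sessions and 1" booster session, and Section 4.2 says that two facilitators "will deliver the 12 sessions". Section 3.3 gives a session length for the existing program ("This is accomplished in 12 two-hour group sessions"). No length is given for CPP-FC.

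Section 4.2 states four purposes for the pilot: acceptability to families, a sound order of material, high caregiver engagement, and feasibility for facilitators. On measurement, Section 4.3 says: "At the end of each CPP-FC session, caregiver participants will complete surveys on satisfaction with session material". It adds homework each week and the Group Environment Scale after sessions 4, 8 and 12. Sections 1.0 and 4.1 name caregiver report and existing electronic databases as the data sources.

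**The concern.** The plan makes a commitment about content and sets a purpose about delivery, but it collects nothing from the people who deliver. Two things are at stake.

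First, the main product of the pilot is feedback that directs further adaptation (Section 14.1). A caregiver who found a topic thin or confusing may be judging the CPP-FC material, or a session in which that material was cut short. The remedies differ: rewrite the content, or change the timing or training. Caregivers new to CPP cannot be expected to know what was left out.

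Second, the case for CPP-FC in Sections 3.2 and 3.3 leans on earlier CPP trials, and the secondary objective is preliminary data for a later trial of CPP-FC. Both are easier to defend if core content was delivered as well as written.

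**Working it through.** No power, alpha or effect-size figure bears on this point, and Section 14.1 rules out inferential statistics. The check sets the commitments beside the listed data.

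**Session count.** 11 weekly + 1 booster = 12 (Section 1.0). This matches the 12 in Section 4.2 and the 12 of the existing program (Sections 2.1 and 3.3). Content is therefore added and modified with no added sessions. With three cohorts, 3 × 12 = 36 sessions at most.

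**What each listed source can show.**

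| Source | Supplied by | Shows | Records components delivered? |
|---|---|---|---|
| Six scales at baseline and end of program (4.3) | Caregiver | Stress, confidence, child behavior | No |
| End-of-session surveys and weekly questionnaires (4.1, 4.3) | Caregiver | Satisfaction, fit to foster care | Indirectly at best |
| Homework (4.3) | Caregiver | Practice at home | No |
| Group Environment Scale, sessions 4, 8, 12 (4.3) | Caregiver | Group environment | No |
| End-of-program satisfaction survey and interview (4.3) | Caregiver | Strengths, difficulties, suggestions | Indirectly at best |
| Epic and IDENTITY (4.1, 4.3) | Existing databases | Child demographics, placement history, services | No |
| Attendance, implied by payment for sessions 1-11 (18.0) | Study payment record | Presence | No |

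**What is not listed.** There is no facilitator log, facilitator survey, adherence checklist, observer rating or session recording. Recording is mentioned only for the qualitative interviews (Sections 10.0 and 19.0). Fidelity is mentioned only in Section 3.1, about a different program.

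**Commitments against data.**
- Core components kept in the written program: covered by the adaptation procedure in Section 4.2.
- Core components kept in delivery: no listed measure.
- Acceptability, order of material and engagement: caregiver measures are listed.
- Feasibility for facilitators: no listed measure.

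**Displacement.** To calculate the share of core content squeezed out, one would need the CPP-FC session length and the minutes taken by the new material. The documents give neither, so no figure can be derived.

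**The case against.** The strongest reply is that the promise to keep core elements concerns design, and Section 4.2 honours it. Core components were identified in step 4, changes that would undermine them are refused, the study team has the final say, a manual is written and facilitators are trained. Verifying fidelity is not among the four pilot purposes. This stands as far as the written program goes, and it limits the point to delivery. It does not supply data on facilitator feasibility, which is one of the four.

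A second reply is that caregiver feedback already helps locate problems. That is right. A reader might infer that results cannot be tied to CPP-FC at all, but the documents do not support this: session surveys, weekly questionnaires and exit interviews all bear on content. They are indirect evidence and cannot verify what was covered.

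A reader might also infer that fixed session time forces core content out, and put a percentage on it. That is not supported. No CPP-FC session length is stated, and some changes modify existing discussion rather than add to it. Pilot cohorts of 6-8 families are also smaller than the 10-15 parents in Section 3.3, which may free discussion time. One caregiver quoted in Table 1 asked for only occasional notes rather than a full session.

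Finally, a reader might expect a delivery record to show whether good results came from the adaptations or from unmodified CPP. It could not, because the pilot has no comparison arm.

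**Conclusion.** The point holds as a gap in measurement of delivery. Of the listed measures, none records which core or adapted components were delivered, and none captures facilitators' view of feasibility. Up to 36 sessions are affected. The documents do not show that core content was lost; they show that the pilot as planned could not tell either way.

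The conclusion assumes that the listed measures are complete. If facilitators already keep a session record that the protocol does not mention, the remaining gap is only to cite it and say how it will be reported.

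The change should be made, but it is modest: the pilot is descriptive and makes no efficacy claim. Its value is to supply data for a stated purpose and to help interpret the feedback that drives further adaptation.

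**What to change.** Add to the end-of-session measures in Section 4.3, for each remaining session: *After each session the two facilitators complete a one-page checklist of that session's CPP core components (as identified in step 4) and CPP-FC adaptations, each marked delivered, shortened or omitted, with session length and a brief rating of feasibility.*

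Add facilitator report to the data sources in Sections 1.0 and 4.1. In Section 14.1, summarise the checklist descriptively by session and cohort, and read it beside session satisfaction and interview themes. State that earlier sessions lack this record.

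**Cost.** Completion time is assumed to be about 5 minutes per session. One cohort would take 12 × 5 = 60 minutes, and the upper limit is 36 × 5 = 180 minutes in all. No new staff, participant burden or inferential analysis is needed.

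**Limits.** The data are self-reported. Coverage across cohorts will be incomplete: the revision history shows two cohorts enrolled by July 2023, and this version is dated October 2023. The documents do not say how many sessions remain.

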# 3.0 Background

### 3.1 Gaps in current knowledge

CPP components address gaps in foster caregiver training to prevent child behavior problems through proactive management. Unfortunately, few existing evidence-based prevention programs are available to foster caregivers. A meta-analysis of foster caregiver and adoptive parent training programs and their effectiveness in modifying child behavior problems identified 29 studies of programs developed or adapted for US foster caregivers. Of those, two group-based caregiver training programs were found to be effective for foster children ages 2-5: Treatment Foster Care Oregon (TFCO) and Parent-Child Interactive Therapy (PCIT). On Poprams require rigorous implementation resources (e.g., a child welfare system trained and maintaining fidelity to implement TFCO; clinicians that accept Medicaid who are trained in PCIT) that can be challenging to maintain, limiting reach and impact in preventing behavior problems among young children and thus reducing placement disruptions. Leveraging programs that can be administered more feasibly (like CPP) may allow resources for PCIT and similar programs to be available for children with more intense needs. CPP fills an important gap by making a prevention program with evidence of effectiveness available to diverse caregivers in a variety of settings, including healthcare. This is particularly relevant for young children in foster care, where challenges related to disrupted routines and inconsistent parenting practices contribute to poorer self-regulation and increased behavior problems. OPP is ideally suited to meet the need for prevention-focused caregiver training to prevent and reduce behavior problems in foster youth.

# 3.2 Relevant preliminary data and relevant prior experience

Effectiveness of CPP in prevention/reduction of behavior problems among at-risk youth. CPP was developed in collaboration with parents of young children (2-5 years of age) residing in Chicago and designed to be delivered during 12 synchronous in-person sessions with groups of parents and two trained facilitators. Parents of young children learn

parenting skills through group discussions, videotaped vignettes of real families managing behavior in real situations, structured role plays, and weekly practice assignments. Video vignettes and structured role plays are used to facilitate discussions around key parenting concepts. CPP has demonstrated effectiveness in reducing behavior problems for children ages 2-5 (N > 500, primarily African American and Latinx youth), with the effect of CPP on reductions in child behavior outcomes 12 months after intervention ranging between d = -0.43 and -0.46. The CPP model has been delivered in a variety of settings, including 5 healthcare systems in the Northeast and Midwest United States.

Asynchronous virtual adaptations of CPP (ezParent) and synchronous virtual adaptations including for our pilot study have been successfully delivered to parents for the past 18 months. Our comparison of virtual and in-person delivery of CPP identified higher percentages of parents completing 6 or more sessions with virtual CPP (47%) vs in-person CPP (36%) and no differences in key outcomes of interest (i.e., caregiver self-efficacy, stress; disruptive child behaviors; ps > .15).

CPP with foster caregivers. We recruited 5 caregivers (100% African American, 60% female) through the CHECK Center (2 licensed, 3 kinship) to participate in CPP virtually beginning in May 2021. Caregivers completed between 9 and 11 sessions (higher than the average of 6.7-7.5 published elsewhere) and all 5 graduated. Increases in confidence in managing challenging behaviors were reported by all 5 caregivers. Median confidence on a 10-point scale was 7 in week 1 and 9 on week 11; all caregivers reported feeling "a little more (40%)" or "much more (60%)" confident in managing children's behaviors at the end of the program, and all caregivers reported improvements in their child's behaviors by the end of the program ("At this point, I feel that my child's behavior is: better [40%]" or "much better [60%]"). All five caregivers reported that the behavior concerns that motivated them to engage in CPP were "much better" at the end of the program. Caregivers also reported that CPP was more effective than other trainings they had received. Caregivers reported that it was "not at all hard [60%]" or "a little hard [40%]" to attend session and complete practice assignments each week.

